9.4. Schematic overview of the data collection & interventions (see next page)

Procedure	Screening (D0 or D1)	D1 ^a	D2	D6	Hospital discharge or D15 ^b	D28 ^c	Follow-up ^d	
Informed consent	X							
Inclusion/exclusion criteria	X							
Randomization		X						
Medical history & biometry	X							
6 minute walk test							X	
Lung function							X	
Physical examination ^h		Per SOC →						
Vital signs ^{e,h}	X	Daily until discharge from hospital →						X
Daily (S)AE inquiry		→						
Concomitant medication	X	→					X ^c	X
ECG ^h	X	On clinical grounds						
Any chest CT scan	X ^p	On clinical grounds						
HRCT ^q							X	
Routine laboratory assessments on clinical grounds, except: - D0/1, D6, discharge/D15 and FU - Procalcitonin 3x/week until D15	X ^{f,h}			X ^{g,h}	X ^g		X ^g	
Study blood sampling^h								
- 2 x 6 ml serum tubes		X		X	X		X	
- 1 x 4 ml EDTA tube (DNA)		X						
- 2 x 10 ml EDTA tube (optional, selected sites)		X		X	X		X	
- 1 x 6 ml EDTA tube (complement)		X	X	X	X			
- 1 x 6 ml EDTA tube for PK (arm A only)		X	X	X	X			
- Arterial blood gas	X ^h			X ^{i,h}	X ⁱ		X	
Score assessments								
- 6-point ordinal scale ^{j,h}		Daily until discharge from hospital →						X
- SOFA score ^{k,h}		X		X	X			
- HScore ^{l,h}		X						
- WHO performance scale ^f							X	
IMP Zilucoplan® (arm A only)		Daily SC until D14 or discharge →						
Third generation cephalosporin (arm A only) ^m		Daily IV until discharge →						
Third generation cephalosporin (arm B only) ⁿ		Daily IV until D7 →						
Oral ciprofloxacin (arm A only) ^o					→ ^o			
Daily drug compliance inquiry		→					X ^c	

^a Prior to first Zilucoplan[®] administration in arm A, and during the day in arm B

^b Hospital discharge or D15, whichever comes first

^c Inquiry by phone on D28 post-randomization (or within next 3 days) for 6-point ordinal scale, (S)AE, supplemental oxygen need (Y/N) and concomitant medication since discharge or D15

^d Follow-up visit at 12-22 weeks post-randomization

^e Values between 7-10AM Includes T°C (actual and highest last 24h), Pulse rate, Blood Pressure, Respiratory Rate, SpO2 by pulseoximetry, FiO2 and ventilator parameters (if patient admitted to ICU) Time window of assessment of vital signs (7-10 AM) is not applicable for follow-up visit.

^f Minimally includes Ferritin, LDH, haptoglobin, D-dimers, CRP, creatinine, triglycerides, fibrinogen, eosinophils, lymphocytes, neutrophils, haemoglobin, WBC count, platelets, bilirubin, ALT and AST, procalcitonin and bHCG (females) (For exclusion criteria, HScore and SOFA)

^g Should minimally include Ferritin LDH, haptoglobin, D-dimers, CRP, creatinine, fibrinogen, eosinophils, lymphocytes, haemoglobin, WBC count, platelets, bilirubin, ALT and AST (For SOFA)

^h If arm A: Pre-dose Zilucoplan[®]

Arterial blood gas: If an arterial blood gas value is available of less than 24 hours before randomization, there's no need to have a new ABG done on Day 0/1.

ⁱ Mandatory: patient in upright position, after minimal 3 minutes without supplemental oxygen. In case of inability to sit upright: same position is to be used for all measurements of PaO2. In ventilated patients PaO2 can be taken from invasive arterial line and FiO2 taken directly from mechanical ventilation settings, document FiO2 at moment of ABG. For patients on ECMO the PaO2/FiO2 ratio and Aa-gradient cannot be calculated as in this case the FiO2 will be missing. Therefore, the last available value of PaO2/FiO2 ratio and Aa gradient prior to ECMO can be used at that timepoint.

^j Defined as 1 = Death; 2 = Hospitalized, on invasive mechanical ventilation or ECMO; 3 = Hospitalized, on non-invasive ventilation or high flow oxygen devices; 4 = Hospitalized, requiring supplemental oxygen; 5 = Hospitalized, not requiring supplemental oxygen; 6 = Not hospitalized

^k SOFA score (see <https://www.mdcalc.com/sequential-organ-failure-assessment-sofa-score>): requires PaO2, FiO2, platelet count, GCS, bilirubin, MAP and creatinine. To be evaluated between 6 and 10 am. Score to be calculated based on the worst values in the previous 24h at time of evaluation.

^l HScore (see <https://www.mdcalc.com/hscore-reactive-hemophagocytic-syndrome>): requires T°C, haemoglobin, wbc count, platelets, ferritin, fibrinogen, triglycerides and AST (BM aspirate is not required) To be evaluated at time of randomization.

^m Third generation cephalosporin replaces empiric amoxicillin/clavulanic acid to treat concomitant community acquired pneumonia. In case of allergies or clinical indication for antibiotic switch, *N. meningitidis* and *S. pneumoniae* need to be covered by the new antibiotic treatment (e.g. meropenem or piperacilin/tazobactam). Third generation cephalosporin is given until D28 or hospital discharge whichever comes first.

ⁿ Group B patients receive daily injection of 2g ceftriaxone IV (or appropriate alternative in case of allergies or on clinical indication) during one week or until hospital discharge, whichever comes first.

^o Upon discharge before D28 post-randomization, patients will switch to daily oral ciprofloxacin (500 mg 1x/d) until at least 14 days after the last dose of Zilucoplan® (only in arm A).

^p any form of chest CT scan within 48h before randomization (low dose, HRCT, or Angio CT scan) must document a presence of bilateral ground glass infiltrates or bilateral consolidation

^q HRCT scoring: A subjective assessment of the overall extent of normal attenuation, reticular abnormalities, honeycombing and traction bronchiectasis will be performed. A reticular abnormality is defined as a collection of innumerable areas of small linear opacity. Honeycombing is defined as the presence of a cystic airspace measuring 3-10 mm in diameter, with 1- to 3-mm thick walls. Traction bronchiectasis is defined as irregular bronchial dilatation within the surrounding areas showing parenchymal abnormalities. The morphological criteria on HRCT scans include bronchial dilatation with respect to the accompanying pulmonary artery, a lack of tapering of the bronchi and the identification of bronchi within 10 mm of the pleural surface. The HRCT findings will be graded on a scale of 1-4 based on the classification system: 1. normal attenuation; 2. reticular abnormality; 3. traction bronchiectasis; and 4. honeycombing. The presence of each of the above four HRCT findings will be assessed independently in three (upper, middle and lower) zones of each lung. The upper lung zone is defined as the area of the lung above the level of the tracheal carina, the lower lung zone is defined as the area of the lung below the level of the inferior pulmonary vein and the middle lung zone is defined as the area of the lung between the upper and lower zones. The extent of each HRCT finding will be determined by visually estimating the percentage (to the nearest 5%) of parenchymal involvement in each zone. The score for each zone will be calculated by multiplying the percentage of the area by the grading scale score. The six zone scores will be averaged to determine the total score for each patient. The highest score is 400 points and the lowest score is 100 points using this calculation method. The total score is the "HRCT fibrosis score". (<https://www.ncbi.nlm.nih.gov/pmc/articles/PMC3922654/pdf/1465-9921-15-10.pdf>)

^r WHO performance scale: 0. Able to carry out all normal activity without restrictions; 1. Restricted in physically strenuous activity but ambulatory and able to carry out light work; 2. Ambulatory and capable of all self-care but unable to carry out any work: up and more than 50% of waking hours; 3. Capable of only limited self-care: confined to bed or chair more than 50% if waking hours; 4. Completely disabled: cannot carry on any self-care: totally confined to bed or chair.

9.5. Restrictions for subjects during the study

There are no subject restrictions during this trial.

10. Sampling

10.1. Types and number of samples

D1: pre-dose serum blood sample 2 x 6ml serum, one EDTA 6ml tube for PK in active group A, one 4 ml DNA EDTA tube, one EDTA 6 ml tube for complement and optional EDTA blood sample, 2 x 10 ml

D2: predose 1 x 6ml EDTA tube for PK in active group A only, 1 x 6ml EDTA tube for patients in both groups

D6: serum blood sample 2 x 6ml serum tube, one 6 ml EDTA tube for PK in group A, 1 x 6ml EDTA tube for patients in both groups and optional EDTA blood sample, 2 x 10 ml

D15 or at discharge: serum blood sample 2 x 6ml, one 6 ml EDTA tube for PK in group A, 1 x 6ml EDTA tube for patients in both groups and optional EDTA blood sample, 2 x 10 ml

Week 12-22 post-randomization follow-up visit: serum blood sample 2 x 6ml, optional EDTA blood sample, 2 x 10 ml

10.2. Timepoints of sampling

These samples are to be taken predose on D1, D2, D6 and D15 (or discharge whichever comes first) and on final follow up visit between week 12 and 22.

10.3. Sample Handling & Analysis

Samples will be taken during hospitalization preferably together with the blood draw for standard of care and will be used for measurements of pharmacodynamics and pharmacokinetic endpoints described under section 4.3

For sample handling and analysis, see lab manual provided by Covance.

OPTIONAL sampling per center

In selected centers (to be decided by the local investigator after consulting with the coordinating principle investigator), additional 2 x 10 ml EDTA blood tubes will be taken at day 1, 6 and 15, or at hospital discharge whichever comes first and safety follow-up, for flow cytometric analysis and COVID-19 related research purposes. The samples will be stored in the FAGG-certified biobank mentioned in section 10.5 until further use in the context of COVID-19 related research takes place.

Separate submission to the Ethics Committee will be initiated before execution of any research activity on the blood samples stored in the biobank.

10.4. Sample Storage and/or shipping

See lab manual provided by Covance.

Optional EDTA samples (selected sites) to be shipped to UZ Ghent for analysis and storage.

10.5. Future use of stored samples

Initially samples will be stored for the use as described within this protocol. If at a later time point samples will be stored for future use, they will be stored in the FAGG certified biobank “prospectieve biobank CF, bronchiëctasieën en respiratoire infecties” managed by biobank manager [name]. [name]. For each future project with samples collected from the current protocol, a separate Ethics Committee approval will be obtained.

11. Statistical Considerations

11.1. Sample size calculation

The outcome(s) on which the sample size calculation is based upon, is the primary endpoint measurement of oxygenation, defined as ratio of PaO₂/FiO₂.

Sample calculation and power analysis have been performed by UCB. The target difference is the difference measured at the primary endpoint (day 6 and day 15 or discharge) between the control and the treated group. Given a sample size of 81 patients, 54 on Zilucoplan[®] and standard of care and 27 on standard of care there would be >85% power to show a significant difference from standard of care at the 2 sided 5% level if the true underlying treatment difference was an 80 point difference (25% of 320, being the mean at hospital admission) in the PaO₂/FiO₂ ratio. This assumes a standard deviation of 105 and a dropout rate of less than 10%.

11.2. Type of statistical methods

All primary and secondary endpoints will be summarized and where relevant represented graphically

Primary endpoint:

The change from baseline in PaO₂/FiO₂ ratio will be analyzed using a Mixed Model Repeated Measures (MMRM) analysis with a fixed effect for Baseline PaO₂/FiO₂ ratio, treatment, day and treatment by day interaction, where day is categorical. Subject will be fitted as a random effect and an unstructured covariance will be used unless it fails to converge, where other covariance structures will be considered. Other covariates, such as gender, may also be included in the model, if by the time of the analysis these have been identified as key differentiators in terms of COVID-19 recovery. If the variability is shown to be inappropriate for this additive model, then a log transformation of the PaO₂/FiO₂ ratio may be considered.

Data from SOC in another study with a very similar protocol may be incorporated into the analysis using a Bayesian frame work. This will be described more fully in the statistical analysis plan (SAP).

A similar analysis for the P(A-a)O₂ gradient will be completed

Other Endpoints:

Other continuous endpoints will be analyzed in a similar way using an MMRM.

Response rates, such as 28 day all-cause mortality a logistic regression will be used.

Count data will use a generalized linear model with a log link unless the model is either over or under dispersed and then an alternative approach will be used. If it is counts out of a fixed number of days, then a logistic regression will be considered.

For the final follow up, a survival analysis with Kaplan-Meir plots will be created covering from Day 1 to end of follow up.

The detail around the analyses will be explained in more detail in the SAP and as this is an exploratory study, additional analyses may be considered to explore the data more fully.

Interim analyses: will be performed when 42 patients have reached primary endpoint analysis.

After half the patients have completed day 15 an interim analysis will be completed to understand if there is already enough evidence to prompt further work on COVID-19 treatment with Zilucoplan®. There is no plan to stop the study at this stage.

Analyses will also be completed when all patients have finished day 28 to assess all pre-follow up assessments and 28 day mortality (via phone call). This will enable key results to be understood as soon as possible without compromising the study.

11.3. Statistical analysis team

The statistical analysis will be performed by UCB.

12. Data handling

12.1. Method of data collection

Subjects that are included in the study at Ghent University Hospital or other Belgian centers, will be assigned a unique study number upon their registration in REDCap. On all documents submitted to the coordinating center, sponsor or CI, patients will only be identified by their study number. The subject identification list will be safeguarded by the site. The name and any other directly identifying details will not be included in the study database.

12.1.1. Case Report Form

An electronic data capture (EDC) system, i.e. REDCap, will be used for data collection. Data reported on each eCRF should be consistent with the source data. If information is not known, this must be clearly indicated on the eCRF. All missing and ambiguous data will be clarified.

Only the data required by the protocol are captured in the eCRF. The eCRFs and the database will be developed, based on the protocol. The final eCRF design will be approved by the Co-ordinating Investigator.

All data entries and corrections will only be performed by study site staff, authorized by the investigator. Data will be checked by trained personnel (monitor, data manager) and any errors or inconsistencies will be clarified. The investigator must verify that all data entries in the eCRF are accurate and correct.

REDCap is provided and maintained by Vanderbilt University; a license for use was granted to the Health, Innovation and Research Institute (HIRUZ). REDCap is a web-based system intended for academic clinical trials.

The study site staff is responsible for data entry in REDCap.

12.1.2. Data directly collected in the CRF (no source available)

All data is to be collected in accordance with the latest version of the ICH E6 (R2) GCP guidelines. There will be no data directly collected in the CRF.

12.2. Data storage

The data is accessed through a web browser directly on the secure REDCap server. The server is hosted within the UZ Ghent campus and meets hospital level security and back-up requirements.

Privacy and data integrity between the user's browser and the server is provided by mandatory use of Transport Layer Security (TLS), and a server certificate issued by TERENA (Trans-European Research and Education Networking Association). All study sites will have access to REDCap. Site access is controlled with IP restriction.

12.3. Archiving of data

The investigator and sponsor specific essential documents will be retained for at least 25 years. At that moment, it will be judged whether it is necessary to retain them for a longer period, according to applicable regulatory or other requirement(s).

12.4. Access to data

Direct access will be granted to authorised representatives from the Sponsor, host institution and the regulatory authorities to permit study-related monitoring, audits and inspections.

Pseudonymized biological analyses, study data and study results will also be shared with the provider of Zilucoplan® (UCB Pharma)

Login in REDCap is password controlled. Each user will receive a personal login name and password and will have a specific role which has predefined restrictions on what is allowed in REDCap. Furthermore, users will only be able to see data of subjects of their own site. Any activity in the software is traced and transparent via the audit trail and log files.

13. Safety

13.1. Definitions

Term	Definition
Adverse Event (AE)	Any untoward medical occurrence in a subject to whom a medicinal product has been administered, including occurrences which are not necessarily caused by or related to that product. An AE can therefore be any unfavourable and unintended sign (including an abnormal laboratory finding), symptom, or disease temporally associated with the use of a medicinal (investigational) product, whether or not related to the medicinal (investigational) product.
Unexpected Adverse Event	An adverse event, the nature or severity of which is not consistent with the applicable product information (e.g., Investigator's Brochure for an unapproved investigational product or package insert/summary of product characteristics for an approved product).
Adverse Reaction (AR)	An untoward and unintended response in a subject to an investigational medicinal product which is related to any dose administered to that subject. The phrase "response to an investigational medicinal product" means that a causal relationship between a study medication and an AE is at least a reasonable possibility, i.e. the relationship cannot be ruled out. All cases judged by either the reporting medically qualified professional or the Sponsor as having a reasonable suspected causal relationship to the study medication qualify as adverse reactions.
Serious Adverse Event (SAE)	
A serious adverse event is any untoward medical occurrence that:
 
 • results in death • is life-threatening • requires inpatient hospitalisation or prolongation of existing hospitalisation • results in persistent or significant disability/incapacity • consists of a congenital anomaly or birth defect 
Other 'important medical events' may also be considered serious if they jeopardise the subject or require an intervention to prevent one of the above consequences.
 
NOTE: The term "life-threatening" in the definition of "serious" refers to an event in which the subject was at risk of death at the time of the event; it does not refer to an event which hypothetically might have caused death if it were more severe.

Serious Adverse Reaction (SAR)	An adverse event that is both serious and, in the opinion of the reporting Investigator, believed with reasonable probability to be due to one of the study treatments, based on the information provided.
Suspected Unexpected Serious Adverse Reaction (SUSAR)	
A serious adverse reaction, the nature and severity of which is not consistent with the information about the medicinal product in question set out:
 
 • in the case of a product with a marketing authorisation, in the summary of product characteristics (SmPC) for that product • in the case of any other investigational medicinal product, in the investigator's brochure (IB) relating to the study in question

Attribution definitions

An adverse event is considered associated with the use of the drug if the attribution is possible, probable or definitive, in the opinion of the investigator.

Not related

An adverse event which is not related to the use of the drug.

Unlikely

An adverse event for which an alternative explanation is more likely - e.g. concomitant drug(s), concomitant disease(s), and/or the relationship in time suggests that a causal relationship is unlikely.

Possible

An adverse event which might be due to the use of the drug. An alternative explanation - e.g. concomitant drug(s), concomitant disease(s), - is inconclusive. The relationship in time is reasonable; therefore the causal relationship cannot be excluded.

Probable

An adverse event which might be due to the use of the drug. The relationship in time is suggestive (e.g. confirmed by dechallenge). An alternative explanation is less likely - e.g. concomitant drug(s), concomitant disease(s).

Definitely

An adverse event which is listed as a possible adverse reaction and cannot be reasonably explained by an alternative explanation - e.g. concomitant drug(s), concomitant disease(s). The relationship in time is very suggestive (e.g. it is confirmed by dechallenge and rechallenge).

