13.7. Development Safety Update Report

The Coordinating Investigator will provide DSURs once a year throughout the entire duration of the clinical study, or on request, to the Competent Authority, Central Ethics Committee and Sponsor. This DSUR will include all SAE's (who were not categorized as SAR's and were not immediately reported to the EC).

The report will be submitted 1 year (+ maximum 60 days) after the 'Development International Birth Date (DIBD)', and will subsequently be submitted each year until the study is declared ended. This DIBD is the date of the sponsor's first overall authorisation to conduct the clinical trial in any country worldwide.

HIRUZ CTU can provide a template that can be used to complete this DSUR.

14. Monitoring/Auditing/Inspection

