2.2.4 Safety endpoint(s)

2.2.4.1 Key safety endpoint(s)

The key safety endpoints of this study are the incidence/number of adverse events (AE), serious adverse events (SAE) and the severity of AEs from first dose of study treatment on D1 until D28. Each AE will be categorized as a Treatment Emergent Adverse Event (TEAE) or not. All cases will be assessed by the reporting medically qualified professional or Sponsor as to having a reasonable suspected causal relationship to study treatment or not and categorized on the eCRF as

1. Not related
2. Unlikely
3. Possible
4. Probable
5. Definitely

All AE/SAEs that fall into the last 3 categories are deemed as related to study treatment and will be classified as an Adverse Reaction (AR) or Serious Adverse Reaction (SAR) respectively.

Each SAEs will also assessed as to whether it was an unexpected SAR (Suspected Unexpected Serious Adverse Event, SUSAR)

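### Protocol 13.1 sets a stricter test for a SUSAR than for an unexpected event, so a serious reaction that is unexpected only in severity has no clearly stated route to the authority

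*Protocol*

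**What the plan says.** Protocol 13.1 gives these definitions close together:

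- Unexpected adverse event: "An adverse event, the nature or severity of which is not consistent with the applicable product information".
- SUSAR: "A serious adverse reaction, the nature and severity of which is not consistent with the information about the medicinal product in question". For a product without marketing authorisation, the reference is the investigator's brochure.
- Adverse reaction: a causal link that "is at least a reasonable possibility, i.e. the relationship cannot be ruled out". The definition takes in "All cases judged by either the reporting medically qualified professional or the Sponsor as having a reasonable suspected causal relationship".
- SAR: an event that is serious and, "in the opinion of the reporting Investigator, believed with reasonable probability to be due to one of the study treatments".
- Attribution scale: an event counts as associated with the drug "if the attribution is possible, probable or definitive, in the opinion of the investigator".

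SAP 2.2.4.1 has the reporting professional or the sponsor rate each event on five levels (not related, unlikely, possible, probable, definite). It then states: "All AE/SAEs that fall into the last 3 categories are deemed as related to study treatment". Serious events in those three categories are SARs.

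The routes are as follows. Under protocol 13.2.2 every SAE goes within 24 hours to the local ethics committee, HIRUZ CTU, the national coordinating investigator and the company. Under 13.2.3 the coordinating investigator, consulting HIRUZ CTU, decides whether an SAE is a SUSAR. If so, it goes to the central ethics committee and the FAMHP, within 7 calendar days if life-threatening or fatal and 15 otherwise. In the 13.4 flowchart only the SUSAR row contains a step to the FAMHP; the SAR row leads to the central ethics committee and the company. The DSUR goes to the competent authority, the central ethics committee and the sponsor, and 13.7 describes its content thus: "This DSUR will include all SAE's (who were not categorized as SAR's and were not immediately reported to the EC".

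**The concern.** The definitions in 13.1 decide which serious reactions are sent to the FAMHP on the 7- or 15-day clock. The test for being unexpected and the test for being a SUSAR differ in one word, *or* against *and*, and that word changes the answer for a whole class of events: known reactions that turn out worse than listed. An event in that class drops back to the SAR row, and the annual report as described does not pick it up. The trial gives a C5 inhibitor in what protocol 13.6 calls a new disease indication, so reactions of unexpected severity matter here.

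A second, smaller mismatch lies in causality. An adverse reaction needs possibility, judged by the investigator or the sponsor. A SAR needs probability, judged by the reporting investigator. An exploratory endpoint in protocol 4.3 is the 28-day incidence of SARs and SUSARs, so the wording bears on an analysis as well as on reporting.

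**Working it through.** No arithmetic applies. The check sets the definitions side by side and then follows each class of event along the written routes.

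**Step 1, expectedness.** Take a serious reaction whose nature is in the investigator's brochure and whose severity exceeds what is listed there. Under the unexpected-event definition one departure is enough, so it is unexpected. Under the SUSAR definition, read literally, both nature and severity must depart; nature does not, so it is not a SUSAR. Protocol 13.5 adds a third statement: a disease-related event that is serious, related and unexpected is reported as a SUSAR. Since 13.1 defines unexpected with *or*, 13.5 does not agree with the SUSAR row either.

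**Step 2, causality.** The adverse-reaction definition, the attribution scale and SAP 2.2.4.1 all admit the rating *possible*. The SAR definition speaks of probability. One of the three ratings that the SAP counts as related is therefore in doubt under the protocol's SAR wording, as is an event that the sponsor alone considers related.

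**Step 3, routes.** The table takes the ethics committee in 13.7 to be the central one.

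| Serious event | Class under 13.1, read literally | Expedited to the FAMHP? | In the DSUR as 13.7 describes it? |
|---|---|---|---|
| Related, nature and severity both inconsistent with the brochure | SUSAR | Yes, 7 or 15 days | Not needed for notification |
| Related, listed nature, greater than listed severity | SAR, unexpected, not SUSAR | No | No |
| Related and expected | SAR | No | No |
| Rated possible, or judged related by the sponsor alone | Adverse reaction or associated event, arguably not SAR | No | Yes, as an SAE |
| Not related | SAE | No | Yes |

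Rows two and three have no clearly stated route to the authority, although an unrelated SAE has one. Row four reaches the authority, but yearly rather than within days.

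**Step 4, loose ends.** The SAE row of the flowchart sends the reader to section 13.8 for the yearly list, but chapter 13 ends at 13.7, so no further section fills the gap. Also, 13.2.2 sends every SAE to the local ethics committee within 24 hours. If that is the committee meant in 13.7, the set described there is empty. The text should say which committee is meant.

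**The case against.** The strongest reply is that the system as a whole is better than its definitions. Every SAE, whatever its causality, reaches HIRUZ CTU, the national coordinating investigator and the company within 24 hours, and 13.2.3 starts the SUSAR decision from the SAE, not from the reporting investigator's SAR label. Protocol 13.5 and SAP 2.2.4.1 both frame the question as whether the event was unexpected, which points to the *or* test. The SUSAR phrase could also be read as one combined profile that fails if either part differs. Finally, 13.7 says what the DSUR will include, not that it is limited to this; reports may also be given on request; and because a SAR is by definition an SAE, the flowchart rows might be cumulative, which would put SARs on the yearly list.

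Much of this stands. It shows that central staff will see the events and may well classify them sensibly. It does not remove the conflict between the two definitions that those staff must apply. Protocol 13.5 covers only disease-related events, and no passage states that SARs enter the DSUR.

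A reader might infer three stronger things that the documents do not support:

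- That the narrow SAR definition itself makes reactions miss the authority. It works the other way: an event not called a SAR remains an SAE and falls within the DSUR as described. The cost is delay.
- That 13.7 restricts the DSUR to SAEs that are not SARs. The limiting word is absent, although the parenthesis reads naturally that way.
- That the protocol and SAP give different SAR counts. Protocol 4.3 has no derivation, and the SAP supplies the only operational rule. The counts could differ if *possible* is taken to fall short of probability; this is not shown.

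**Conclusion.** The point holds as an internal contradiction in a safety-reporting rule. Read literally, 13.1 leaves a serious reaction that is unexpected in severity alone outside expedited reporting to the FAMHP, and neither 13.4 nor 13.7 gives that reaction, or an expected SAR, a clearly stated route to the authority. The SAR causality wording is a separate and lesser inconsistency that could delay a report or alter the SAR/SUSAR count.

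The size is limited to classes of event; the documents give no frequency. As an illustration only, protocol 8.1.8 treats greater susceptibility to encapsulated bacteria under C5 inhibition as established. If the investigator's brochure lists serious infection, which is an assumption, then an infection worse than listed is exactly the case on which the two definitions disagree.

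The conclusion rests on the literal reading of *and*, on the natural reading of the parenthesis in 13.7, and on the ethics committee there being the central one. It uses no outside regulation.

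**What to change.** Amend the protocol as follows:

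1. In 13.1, define a SUSAR as a SAR whose nature *or* severity is not consistent with the reference product information.
2. In 13.1, define a SAR as a serious AE rated possible, probable or definite by the investigator or the sponsor. This matches the adverse-reaction definition, the attribution scale and SAP 2.2.4.1, and leaves one basis for the SAR/SUSAR endpoint in 4.3.
3. In 13.7, state that the DSUR covers all SAEs, including SARs and SUSARs already sent to an ethics committee. This also settles which committee the parenthesis refers to.
4. In 13.4, replace the reference to section 13.8 with 13.7.

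The cost is one amendment and possibly a few more expedited reports. SAP 2.2.4.1 can stay as it is.
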